Design: Pilot of novel care model for low-barrier care and adherence support for uptake and sustained use of biomedical HIV prevention and medications for opioid use disorder for women who inject drugs

Study Population: 50 female-identifying people ≥18 years of age and older who have ever injected drugs and are not known to be HIV-positive

Study Site: Community-based clinic on north Aurora Avenue in Seattle, WA

Primary Study Objectives:

1. Evaluate uptake of PrEP and MOUD
2. Evaluate sustained use of PrEP and MOUD
3. Evaluate treatment completion rate and time to completion after POC STI testing
4. Assess acceptability of pilot community-based care model
5. Assess acceptability of POC STI testing at community-based site.

Approach: We will conduct a pilot study of a community-based novel care model developed with community feedback and a community advisory board (CAB) co-design process during phase I of this project. We will enroll 50 female-identifying people and follow them for 6 months. We will assess uptake of PrEP and buprenorphine; POC STI testing and treatment completion rates; sustained use of PrEP and buprenorphine at months 3 and 6 (n=50). We will conduct surveys, guided by CFIR, to assess and characterize the acceptability and feasibility of venue-based primary and HIV prevention care among women who inject drugs (WWID).

Background and rationale

Women who inject drugs (WWID) experience frequent barriers to receiving primary care, especially sexual health and addiction services, because of perceived stigma, competing needs, and structural inequities within the healthcare system. Barriers to care among WWID are often exacerbated by the additional social chaos of unstable housing and engagement in transactional sex. These structural realities promote exclusion from traditional primary care systems, increase risk of HIV acquisition, and have led to rising rates of syphilis infections and overdose deaths among WWID in recent years. PrEP, buprenorphine, and STI control are key components of the End the HIV Epidemic prevention pillar and proven tools for reducing risk of HIV acquisition and opioid overdose, but uptake and sustained use of these interventions are low among WWID.

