All female identifying persons who present to the venue-based clinic will be eligible for receipt of HIV and STI testing, as well as oral PrEP and MOUD, regardless of participation in the research study. Similarly, study participants will be eligible for care if they visit the venue-based clinic for interim visits outside of their designated study visits (e.g., baseline, 3-months, 6-months, monthly refills for buprenorphine). Standard of care will include checking vital signs, addressing any immediate health concerns as able/feasible within the van clinic, laboratory-based HIV screening, laboratory-based STI testing, and prescription of oral PrEP and/or MOUD, though many services will require billing and insurance claims through the healthcare system and women will be made aware of these prior to initiating these services (e.g., laboratory-based testing, prescription drugs) (Table 1).

Table 1. Study Procedures					
Study Visit Month		0	3	6	Refill visits and Interim non-study visits
General Research Activities					
	Obtain informed consent	X			
	Screen for inclusion/exclusion	X			
	Collect updated contact information	X	X	X	X
	Reimbursement	X	X	X	
Research Questionnaires					
	Demographic information	X			
	Behavior (sexual and drug use and risk perception)	X	X	X	
	Adherence to PrEP and/or MOUD		X ^b	X ^b	
	Acceptability of venue-based care	X	X	X	
	Health and acute healthcare need	X	X	X	X
	Provider clinical summary report	X	X	X	X
Standard of care					
	Medication review	X	X	X	X
	General symptom assessment	X	X	X	X
	Blood pressure checks	X	X	X	X
	Supply condoms	X	X	X	X
	Contraception counseling and provision/referral	X ^{ab}	X ^{ab}	X ^{ab}	
	Laboratory Pregnancy testing	X ^{ab}	X ^{ab}	X ^{ab}	X ^{ab}
	Narcan prescription	X ^a	X ^a	X ^a	X ^{ab}
	Laboratory HIV test	X ^{ab}	X ^{ab}	X ^{ab}	X ^{ab}
	Laboratory STI (CT/GC and TV) genital testing	X ^{ab}	X ^{ab}	X ^{ab}	X ^{ab}
	Laboratory STI (CT/GC) pharyngeal and rectal testing	X ^{ab}	X ^{ab}	X ^{ab}	X ^{ab}
	Laboratory Syphilis testing (IgG and/or RPR)	X ^{ab}	X ^{ab}	X ^{ab}	X ^{ab}

	Laboratory Hepatitis B serologies	X ^{ab}			
	Laboratory Creatinine check	X ^{ab}		X ^{ab}	
	Laboratory Hepatitis C testing	X ^{ab}			X ^{ab}
	Suboxone prescription	X ^{ab}	X ^{ab}	X ^{ab}	X ^{ab}
	PrEP prescription	X ^{ab}	X ^{ab}	X ^{ab}	X ^{ab}
	STI treatment	X ^{ab}	X ^{ab}	X ^{ab}	X ^{ab}
	Referral to specialty care	X ^{ab}	X ^{ab}	X ^{ab}	X ^{ab}
Research Clinical Care					
	POC HIV/Syphilis testing (rapid test)	X	X	X	

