POC STI test for *T. vaginalis* will be available within 10 minutes using individual FDA approved, CLIA waived lateral flow OSOM tests. This trichomonas rapid antigen test does not require equipment or a machine to process and is an immunochromatographic capillary-flow enzyme immunoassay based on trichomonas membrane proteins. Women will be instructed on self-collection of vaginal swab specimens. OSOM swabs will be placed into a sterile tube and processed on site. Results will be delivered in real-time and no samples will be stored.

Syphilis testing:

A rapid combination HIV/syphilis test (Chembio Diagnostic Systems) will be used to evaluate for *Treponema pallidum* antibodies. Any positive syphilis antibody test will be followed by laboratory-based confirmatory testing. Using shared decision making empiric treatment may be given (or initiating depending on stage of syphilis) prior to receiving confirmation of diagnosis.

HIV testing:

A rapid combination HIV/syphilis test (Chembio Diagnostic Systems) will be used to evaluate for incident HIV infections. Samples will be processed using the Chembio microreader kit. Any positive HIV test will be considered a possible seroconversion. Participants will be counseled on unconfirmed possible HIV diagnosis, the need to stop taking PrEP, and the need for laboratory-based confirmatory testing, which can be drawn on-site. All questions on HIV and HIV testing will be answered. Laboratory-based 4th generation HIV Ab/Ag test and HIV viral load will be drawn with samples sent to Harborview Medical Center, and participants will be linked to the SHE Clinic for next day follow-up.

Laboratory studies for clinical care:

Phlebotomy samples for standard of care labs will be centrifuged (as indicated), labeled, and transported back to Harborview Medical Center (HMC) on ice, where they will be delivered directly to the HMC lab for processing. Results will be reported out in the electronic medical record (EMR). The research team medical provider will call patients to deliver critical and urgent results. If the patient/participant is not reachable by phone, the research team medical provider will enlist the assistance of SHE Clinic staff to help in locating the patient/participant. Patients/participants will be asked to return the venue-based clinic the following week, or they can present to SHE Clinic during daytime hours, to follow-up on results.

Management of new diagnoses

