 - b. Participants who accept prescriptions for MOUD at multiple points throughout the study will only be counted once when calculating uptake.
 - c. Final analysis will present uptake as a percentage (proportion).
3. Evaluate sustained use of PrEP
 - a. PrEP: Dried blood spot (DBS) samples were obtained at each visit to assess PrEP adherence via tenofovir-diphosphate (TFV-DP) concentrations. Sustained use was defined as >4 doses/week, resulting in a DBS TFV-DP concentration of >700 fmol/sample at 3 and/or 6 months post-enrollment among those prescribed PrEP at a preceding study visit.
 - b. Final analysis will present sustained use for both PrEP as a percentage (proportion).
4. Evaluate sustained use of MOUD
 - a. MOUD: DBS samples were obtained at each visit to assess MOUD adherence via buprenorphine and norbuprenorphine concentrations, both measured in ng/mL. Sustained use was defined as any buprenorphine and/or norbuprenorphine detected, resulting in a DBS >0 ng/mL concentration of buprenorphine and/or norbuprenorphine at 3 and/or 6 months post-enrollment among those prescribed MOUD at a preceding study visit.
 - b. Final analysis will present sustained use for MOUD as a percentage (proportion).
5. Evaluate STI treatment completion rate and time to completion after POC STI testing
 - a. Treatment completion will be defined as documented treatment following a reactive POC STI test (chlamydia, gonorrhea, syphilis, and/or trichomonas). Treatment will either be indicated in the Visit Clinical Summary from the study visit or noted during medical record chart review by a study provider. If treatment

was not provided on the same day as the visit, the date of treatment will be documented in the study database.

- b. Final analysis will present the treatment completion rate as the proportion of STIs where treatment was documented, by all STIs and by type.
 - c. Final analysis will present the time to treatment completion as the proportion of STIs treated same-day. Of the STIs not treated same-day, time to treatment will be presented as median number of days with an interquartile range.
6. Assess acceptability of pilot community-based care model
- a. Participants completed an acceptability survey following each study visit. Acceptability will be presented by study visit (i.e., enrollment, Month 3, and Month 6) as a proportion of all enrolled participants (N=50) who responded to the following questions:

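### The STI treatment completion rate opens a syphilis case on a reactive rapid antibody test that the protocol itself sends for confirmation, so reactive results needing no treatment can enter the denominator

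*Protocol*

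**What the plan says.** The Protocol's list of primary objectives includes, as the third: "Evaluate treatment completion rate and time to completion after POC STI testing". Analysis Plan item 5a sets the definition: "Treatment completion will be defined as documented treatment following a reactive POC STI test (chlamydia, gonorrhea, syphilis, and/or trichomonas"). Item 5b gives the rate: "Final analysis will present the treatment completion rate as the proportion of STIs where treatment was documented, by all STIs and by type". Item 5c adds timing: "Final analysis will present the time to treatment completion as the proportion of STIs treated same-day". Item 5 does not define an STI in any other way.

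The Syphilis testing text under Lab Processing and Results Delivery describes the test: "A rapid combination HIV/syphilis test (Chembio Diagnostic Systems) will be used to evaluate for" *Treponema pallidum* antibodies. It continues: "Any positive syphilis antibody test will be followed by laboratory-based confirmatory testing". By shared decision, "empiric treatment may be given (or initiating depending on stage of syphilis) prior to receiving confirmation of diagnosis".

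Table 1 schedules the rapid HIV/syphilis test at Months 0, 3 and 6. Its row "Laboratory Syphilis testing (IgG and/or RPR") carries two footnotes, one limiting the test to women who consent to billing and one to clinical indication.

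**The concern.** The protocol handles a reactive rapid syphilis result as provisional in its clinical sections and as a case in its Analysis Plan. No confirmation step is described for the rapid chlamydia, gonorrhea or trichomonas tests, so the mismatch is confined to syphilis.

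A reactive syphilis result that turns out to need no treatment is scored as a failure if nobody treats it and as a success if it was treated empirically. Neither score says anything about whether infections were treated. The syphilis row, the pooled rate and the same-day share of a primary objective are all exposed. The same-day share is the most awkward: laboratory samples leave for Harborview after the session and patients are asked back the following week or to the SHE Clinic, so confirmation is not available during the visit. For syphilis, same-day treatment largely records how often empiric treatment was chosen.

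Items 1b and 2b say that repeat prescriptions count once. Item 5 has no such rule for a woman who is reactive at more than one visit.

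**Working it through.** The protocol states no expected STI rate, syphilis reactivity, treatment rate or attendance, so there is no figure of its own to reproduce. The check is ratio arithmetic on assumed inputs.

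**From the Protocol.** 50 participants and three visits with rapid testing give at most 50 × 3 = 150 rapid syphilis results.

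**Assumed.**
- T: infections of all types that need treatment
- t: share of T that is treated
- U: reactive syphilis results that need no treatment
- e: share of U treated empirically

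**Formulas.**
- Rate with every reactive result as a case: (T·t + U·e) / (T + U)
- Rate on infections needing treatment: t
- Difference: U·(e − t) / (T + U)

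The difference is zero only if U = 0 or e = t. It is negative when e < t and positive when e > t.

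**All-STI rate.**

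| T | t | U | e | All reactive results as cases | Infections needing treatment |
|---|---|---|---|---|---|
| 20 | 100% | 3 | 0 | 20/23 = 87.0% | 100% |
| 20 | 100% | 6 | 0 | 20/26 = 76.9% | 100% |
| 40 | 100% | 3 | 0 | 40/43 = 93.0% | 100% |
| 40 | 100% | 6 | 0 | 40/46 = 87.0% | 100% |
| 20 | 90% | 3 | 0 | 18/23 = 78.3% | 90% |
| 20 | 90% | 6 | 0 | 18/26 = 69.2% | 90% |
| 20 | 90% | 3 | 100% | 21/23 = 91.3% | 90% |
| 20 | 90% | 6 | 100% | 24/26 = 92.3% | 90% |

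The downward shift is 7 to 23 points in these cases. The upward shift is 1 to 2 points, because a treatment rate already near 100% leaves little room above it.

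**Syphilis row, with and without repeat counting.** Assume 5 infections, all treated, and 2 women reactive without needing treatment and left untreated.
- Each woman counted once: 5 / (5 + 2) = 71.4%.
- The 2 women reactive and counted at all three visits: 5 / (5 + 2 × 3) = 45.5%.
- Infections needing treatment: 5/5 = 100%.

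The repeat-visit line also assumes that the test stays reactive, a point on which the protocol is silent.

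**The case against.** The best defence is that item 5a defines the numerator event, while item 5b divides by STIs, not by reactive tests. Elsewhere the protocol ties treatment to a diagnosis (Follow-up study visits; Management of new diagnoses), so a reader could take STIs in item 5b to mean diagnosed infections. This stands in part: counting every reactive result is the natural reading of item 5, not a literal statement. But if item 5a is not the case definition, item 5 has none for syphilis.

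Second, counting from the reactive test has merit. The objective concerns completion after POC testing, and that denominator keeps women who are lost before confirmation. A denominator limited to laboratory-classified infections would drop them, together with women who do not consent to billing. This stands, and it shapes the fix.

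Third, the harm is contained. Results are also shown by type, so the chlamydia, gonorrhea and trichomonas rates are untouched, and these are descriptive proportions in a 50-person pilot with no test or threshold attached. This stands and limits the severity.

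Fourth, confirmation and repeat-event rules often sit in an SAP. That does not dispose of the point, because the protocol has its own Analysis Plan and fixes the case-opening event there.

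A reader might infer more: that the plan expressly counts every reactive result at all three visits, and that the syphilis rate could collapse. For example, 8 women reactive at every visit, of whom 3 are infected and treated once and 5 need no treatment, would give 3 / (8 × 3) = 12.5%. The documents do not support this. Counting at three visits follows only from Table 1 plus the missing count-once rule, and the example stacks full attendance, persistent reactivity and no empiric treatment of the 5, none of which the protocol states.

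**Conclusion.** The point holds in a limited form. Item 5's only case definition is the reactive POC test, and for syphilis that conflicts with the protocol's own confirmation step. On the natural reading, reactive syphilis results that need no treatment enter the syphilis, all-STI and same-day figures of primary objective 3, possibly more than once per woman. They pull the rates down if untreated and can push them up if treated empirically.

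The size cannot be derived from the protocol. With an assumed 20 infections needing treatment, all treated, 3 to 6 such untreated results give 87% to 77% instead of 100%. With 40 infections the same counts give 93% to 87%. The direction depends on how often empiric treatment is given.

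This should be corrected before analysis, but it does not threaten the study. A reader might go further and conclude that the rule rewards unneeded treatment; nothing in the protocol links this proportion to clinicians' decisions.

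**What to change.** Amend items 5a to 5c as follows.

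1. Keep the reactive POC test as the denominator for chlamydia, gonorrhea and trichomonas.
2. For syphilis, make the main denominator those reactive results that confirmatory testing or clinician chart review classifies as an infection requiring treatment, with each infection counted once.
3. Put reactive syphilis results that are never classified (woman lost, or no laboratory test) in a separately reported category, with a sensitivity analysis that counts them as untreated infections.
4. Also report the rate over all reactive rapid syphilis results, with the numbers confirmed, judged not to need treatment, and treated before confirmation.

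The Syphilis testing text (confirmation of every positive) and Table 1 (laboratory syphilis testing subject to billing consent) must be reconciled, since the classification depends on whether that test is done.

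The cost is a smaller syphilis denominator and some added classification work in the chart review that item 5a already uses. The change concerns counting only and leaves clinical management as it is.

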Participants found to have a diagnosis of chlamydia, gonorrhea, trichomoniasis, or syphilis will be offered prompt treatment. Treatment of gonorrhea will consist of intramuscular ceftriaxone 500mg x1 provided in clinic. Participants who test positive for chlamydia will be recommended to take doxycycline 100mg PO BID for 7 days; however, azithromycin 1g PO x1 will be offered as an alternative if participants are unable to complete a 7-day course of antibiotics. Similarly, participants who test positive for trichomonas will be recommended to take metronidazole 500mg PO BID for 7 days; however, metronidazole 2g PO x1 will be offered as an alternative if participants are unable to complete 7 days of antibiotics. Early syphilis will be treated with 2.4 million units of benzathine penicillin x1 or oral doxycycline 100mg BID for 14 days, pending benzathine penicillin availability. Late latent syphilis will be treated with 2.4 million units of benzathine penicillin weekly for 3 weeks or oral doxycycline 100mg BID for 28 days, pending benzathine penicillin availability. Single dose medications will be available in clinic. Otherwise

prescriptions will be sent to the Harborview Long-term Care Pharmacy for delivery to SHE Clinic within 48 hours. Participants with clinical concern for complicated STI (i.e., PID) will be offered prolonged treatment (single dose IM ceftriaxone and 2-week course of doxycycline and metronidazole) and referred for prompt follow up in SHE Clinic, another primary care clinic, or urgent care as indicated. Participants will be encouraged to tell partners to also be treated and made aware that these are reported by the lab to public health department. Should patients develop signs or symptoms of an STI at any point in the study they may come to the study clinic for additional laboratory-based testing (including for BV or candida infections) and treatment if needed.

Management of HIV

Patients who test positive for HIV on rapid or follow-up laboratory-based testing will be counseled on strategies to prevent transmission and referred to SHE Clinic for urgent evaluation and initiation of antiretroviral therapy, per clinical guidelines.

Management of pregnancy

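### STI treatment completion counts every reactive syphilis rapid test, although the protocol treats that result as unconfirmed and makes earlier treatment optional

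*Protocol*

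**What the plan says.** Primary objective 3 of the protocol concerns the treatment completion rate, and the time to completion, after point-of-care (POC) STI testing. Item 5 of the Analysis Plan turns it into numbers.

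- Item 5a, the event: "Treatment completion will be defined as documented treatment following a reactive POC STI test (chlamydia, gonorrhea, syphilis, and/or trichomonas". Besides the visit summary, treatment may be "noted during medical record chart review by a study provider".
- Item 5b, the rate: "Final analysis will present the treatment completion rate as the proportion of STIs where treatment was documented, by all STIs and by type".
- Item 5c, timing: "Final analysis will present the time to treatment completion as the proportion of STIs treated same-day", with median days and interquartile range for the rest.

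The clinical sections handle syphilis differently from the other three infections. Under Lab Processing and Results Delivery, Syphilis testing, the rapid test looks for *Treponema pallidum* antibodies. Then: "Any positive syphilis antibody test will be followed by laboratory-based confirmatory testing". On treatment in the meantime: "Using shared decision making empiric treatment may be given (or initiating depending on stage of syphilis) prior to receiving confirmation of diagnosis". Under Management of new diagnoses: "Participants found to have a diagnosis of chlamydia, gonorrhea, trichomoniasis, or syphilis will be offered prompt treatment". The POC testing text states no confirmation step for chlamydia, gonorrhea or trichomonas.

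**The concern.** Item 5 gives one trigger, a reactive POC test, and applies it to all four infections alike. Nothing in it mentions confirmation. For syphilis, the protocol's own clinical rules make a reactive rapid test a provisional result: confirmation must follow, and treating before it is a shared decision.

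A clinician who waits, receives a result that does not confirm syphilis and withholds treatment has followed the protocol, yet item 5 as written records a failure. A woman treated empirically whose result is later not confirmed is recorded as an STI successfully treated. The syphilis rate, and the all-STI rate that includes it, would then mix missed treatment of infection with treatment that proved unnecessary. The two errors run in opposite directions and the report would show neither component, so a reader could not correct the figure.

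**Working it through.** **Step 1. How item 5 as written scores each syphilis reactive**

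| Laboratory confirmation | Treated? | Scored under 5a and 5b | Fits the clinical course? |
|---|---|---|---|
| Confirmed | Yes | Completion | Yes |
| Confirmed | No | Missed treatment | Yes |
| Not confirmed | No | Missed treatment | No: treatment was properly withheld |
| Not confirmed | Yes, empirically | Completion (same-day in 5c if given at the visit) | No: no confirmed infection was treated |
| Not done | Either | Completion or missed treatment | Reasonable: the pathway was or was not completed |

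Rows 3 and 4 are the problem.

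**Step 2. Syphilis line.** The protocol states no figure to reproduce and gives neither a reactivity nor a confirmation rate. Table 1 schedules the rapid test at Months 0, 3 and 6, so at most 50 × 3 = 150 tests feed item 5; that is a ceiling on tests, not a count of reactives. The quantities below are assumptions.

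- f: share of syphilis reactives that laboratory testing did not confirm
- p: completion among all other syphilis reactives
- q: share of the non-confirmed reactives that were treated empirically

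Reported rate = (1 − f)p + fq. Difference from p = f(q − p). With p = 80% and q from 0 to 1:

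| f | Lowest (q = 0) | Highest (q = 1) | Difference from 80% |
|---|---|---|---|
| 10% | 0.90 × 0.80 = 72% | 0.72 + 0.10 = 82% | −8 to +2 points |
| 25% | 0.75 × 0.80 = 60% | 0.60 + 0.25 = 85% | −20 to +5 points |
| 50% | 0.50 × 0.80 = 40% | 0.40 + 0.50 = 90% | −40 to +10 points |

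The same formula governs the same-day proportion in 5c, with p and q replaced by the corresponding same-day shares.

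**Step 3. All-STI total.** Let s be the share of all reactives that are syphilis, and r = 90% the completion for the other three infections (both assumed).

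Reported = (1 − s)r + s[(1 − f)p + fq]. With non-confirmed syphilis removed = [(1 − s)r + s(1 − f)p] / (1 − sf).

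- s = 25%, f = 10%: 0.675 + 0.25 × (0.72 to 0.82) = 85.5% to 88.0%, against 0.855 / 0.975 = 87.7%.
- s = 25%, f = 25%: 0.675 + 0.25 × (0.60 to 0.85) = 82.5% to 88.8%, against 0.825 / 0.9375 = 88.0%.
- s = 50%, f = 50%: 0.45 + 0.50 × (0.40 to 0.90) = 65% to 90%, against 0.65 / 0.75 = 86.7%.

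**Step 4. In counts (assumed).** Take 10 syphilis reactives, 5 confirmed, 4 of those treated. If the other 5 are not confirmed, removing them gives 4/5 = 80%; item 5 as written reports 4/10 = 40% if none of them is treated and 9/10 = 90% if all are. If instead the other 5 were never tested further and never treated, 4/10 = 40% is a fair description of follow-through, and a confirmed-only rate of 80% would hide the loss.

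**The case against.** The strongest reply is that the reactive-test trigger fits the objective. Objective 3 is about what happens after POC testing, and the background presents rapid testing as a remedy for loss to follow-up and missed treatment. The section on the Month 3 and Month 6 visits has participants tested by POC and anyone diagnosed treated before leaving, so the rapid result is meant to be acted on at the visit. Counting every reactive measures that test-and-treat pathway. This stands: the all-reactive rate is legitimate and should be kept.

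A second reply is that 5b and 5c speak of STIs, which could mean diagnosed infections, so non-confirmed reactives might never enter the denominator. That reading is possible, but nothing in item 5 states it and the only trigger given is the reactive test. Two analysts could derive different rates from the same records. Nor is this merely detail left to a statistical analysis plan: the protocol states the definition itself, and it does not fit its own syphilis testing rule.

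A third reply is that the consequences are contained. This is a descriptive pilot, item 5 sets no comparison or threshold, and 5b already reports by type, so any distortion is confined to one row and the totals. That is true, and it limits the weight of the point.

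A reader might infer that completion should be restricted to laboratory-confirmed syphilis. The documents do not support that: such a rate conditions on a step after the POC test and drops women lost before confirmation, whose follow-through is part of what the objective measures.

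**Conclusion.** The point holds as a mismatch between the stated definition and the protocol's syphilis testing rule. Read as written, item 5 scores a non-confirmed, properly untreated reactive as missed treatment and a non-confirmed, empirically treated one as a completion. It reaches the syphilis line and the all-STI totals in 5b and 5c, and leaves the chlamydia, gonorrhea and trichomonas lines untouched.

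The size is unknown. A reader might take the wide ranges above as an estimate of bias, or infer that the rates will be too low. Neither is supported: f, p, q, r and s are all assumed, the widest ranges need half of syphilis reactives to go unconfirmed, and the sign depends on whether q lies below or above p. At f = 10% the syphilis figure moves by −8 to +2 points and the all-STI figure at s = 25% by about −2.2 to +0.3 (85.5 − 87.7 and 88.0 − 87.7). If every reactive is confirmed, or if q equals p, the syphilis completion rate is not distorted. The case for a change rests on the ambiguity in a primary objective and the low cost of removing it.

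**What to change.** Add syphilis confirmation status (confirmed, not confirmed, not done) as a field in the chart review that item 5a already plans. The laboratory results should be there to abstract: "Results will be reported out in the electronic medical record (EMR". The visit summary report as described lists POC results but not confirmation, so the field has to be added deliberately. State which laboratory result counts as confirmation, since the syphilis testing paragraph names no assay and Table 1 lists IgG, RPR or both.

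In items 5b and 5c, report the syphilis and all-STI completion and same-day proportions two ways, side by side:

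1. over all reactive POC tests;
2. excluding syphilis reactives that laboratory testing did not confirm, with *not done* cases kept in the denominator so that women lost before confirmation still count.

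Show the treated and untreated counts for each confirmation status.

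The cost is one extra abstracted field, a short addition to item 5, and a somewhat smaller syphilis denominator in the second version. The first version keeps the full count.
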